6.5.5 Endometrial Health Assessment

Ultrasound results (endometrial thickness) will be summarized using mean, standard deviation, minimum, maximum and median by treatment group and visit. The within-subject change will be calculated per visit as the post-baseline measurement minus the baseline measurement and summarized by treatment group and visit. For change from baseline in endometrial thickness, an ANCOVA model, with treatment and strata smoking status (current vs former/never) as factors, with baseline weight and baseline value as covariates, will be used for treatment comparisons.

The descriptive reasons for not evaluable biopsy will be summarized. It includes reasons of not done from eCRF page, reasons of not done from lab and pathologiest readings.

For all postbaseline biopsies, the concordance of 2 of the 3 pathologists reviews will be accepted as the final diagnosis. If there is no agreement among the three pathologists, the most severe diagnosis will then be used as the final diagnosis.

The satisfactory endometrial biopsy results will be summarized for the endometrial health set (EH set). EH set consists of all subjects who are randomized and receive at least one dose of study drug, had the postbaseline biopsy done within 30 days after the last dose of study drug, and

- had an acceptable biopsy at Baseline (at least one endometrial biopsy with satisfactory tissue and no read of hyperplasia, disordered proliferative pattern or malignant); and
- had an satisfactory endometrial biopsy result after or on Day 326 or had a postbaseline final diagnosis of hyperplasia, disordered proliferative or malignant prior to Day 326.

Baseline biopsy is the last non-missing value on or prior to first dose of study drug. When more than one biopsy results are present at postbaseline, if no final diagnosis of hyperplasia, disordered proliferative pattern or malignant, the last non-missing satisfactory result within the window will be counted; otherwise, the more severe result will be counted. For percentage of subjects with final diagnosis of endometrial hyperplasia, percentage of subjects with endometrial cancer, and percentage of subjects with disordered proliferative endometrium, the exact (Clopper-Pearson) upper one sided 95% confidence interval will be provided.

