5.6 Biopsies

5.6.1 Endometrial Biopsy

Subjects will undergo a suction endometrial biopsy at the following time points:

- Screening
- At week 52/EOT
- ED
- All cases of uterine bleeding during treatment

The screening endometrial biopsy must be evaluable.

Subjects that require a retest biopsy, for insufficient material or unevaluable only, will have an extended screening period and will be allowed an additional 15 days of screening (i.e., days -50 to -1). A maximum of 1 retest biopsy during screening is allowed.

Screening biopsy results are valid for study entry for up to 3 months from date of procedure for applicable subjects.

An endometrial biopsy is required at EOT or ED. For EOT/ED week 52 (visit 15) biopsies that are evaluated as insufficient material or unevaluable, a retest biopsy will be required. Any of the three pathologists can determine if a an EOT/ED is insufficient or unevaluable. However, if two pathologists read the EOT/ED endometrial biopsy as evaluable and issue the same diagnosis, and the 3rd pathologist reads the biopsy as insufficient or unevaluable, the biopsy does not need to be repeated.

During the treatment period, any woman with an abnormal endometrial biopsy reported as disordered proliferative endometrium, endometrial hyperplasia or endometrial cancer will be referred to standard of care clinical management and followed to resolution, and the report of any medical or surgical procedures and the resultant pathology will be obtained. The

investigator should record any such biopsy, and the associated diagnostic and therapeutic measures, as an AE.

Subjects with endometrial fibroids may be included in the study provided the endometrial biopsy result at screening is satisfactory and the investigator is confident no treatment will be required during the study.

Subjects will be allowed entry into the study on the primary endometrial result/diagnosis. A secondary and tertiary endometrial diagnosis will also be reported. A subject should discontinue the study if secondary or tertiary endometrial biopsy diagnosis is Category 2. All 3 pathology reports should be filed in the subject's source document. Please reference the central laboratory manual for further details and timing of biopsy specimen results.

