3 SAMPLE SIZE

The primary objective of this study is to assess long-term safety and tolerability. The sample size in this study is not calculated based on the statistical power for efficacy evaluation to detect treatment difference.

The total of 1740 subjects are planned to be randomized 1:1:1 to the fezolinetant 45 mg once daily group (580), fezolinetant 30 mg once daily group (580), or placebo group (580). This sample size would provide high probability to observe events of special interest that has a

		Per Treatment Arm		
Sample Size (1:1:1)	n = 580			
Background Event Rate	Prob(#>=3)	Prob(#>=2)	Prob (#>=1)	
0.10%	2.11%	11.53%	44.03%	
0.20%	11.18%	32.29%	68.69%	
0.30%	25.33%	51.94%	82.49%	
0.40%	40.94%	67.43%	90.22%	
0.50%	55.46%	78.62%	94.54%	
0.60%	67.63%	86.28%	96.95%	
0.70%	77.16%	91.35%	98.30%	
0.80%	84.27%	94.62%	99.05%	
0.90%	89.38%	96.69%	99.47%	

fairly low background event rate of less than 1%. With the sample size, the following table illustrates the probability of observing 1 or more events, 2 or more events and 3 or more for different background event rates ranging from 0.10% to 0.90%.

Prob(#>=1) means the probability of observing 1 or more events.

Prob(#>=2) means the probability of observing 2 or more events.

Prob(#>=3) means the probability of observing 3 or more events.

In addition, with an assumed background rate of 0.26% such as for endometrial hyperplasia, this sample size would provide the final number of evaluable subjects demonstrate that the point estimate for the rate of the event is less than or equal to 1% and the upper bound of the one-sided 95% confidence interval is less than or equal to 4% (as recommended in the FDA guidance on Estrogen and Estrogen/Progestin Drug Products to Treat Vasomotor Symptoms) with greater than 95% probability assuming up to 60% (including baseline, ED and subject refusal of endometrial biopsy at EOT) of subjects may not have evaluable biopsy data.

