6.5.1 Adverse Events

Per protocol, a treatment emergent adverse event (TEAE) is defined as the AEs that occurred on or after first dose of study drug and 21 days after the last dose of study drug (when AE collection closes).

A study drug-related TEAE is defined as any TEAE with a causal relationship of YES by the investigator.

The sponsor has a list of events that they classify as "always serious" events. If an AE is reported that is considered by the sponsor to be an SAE per this classification as "always serious", the AE will be treated as an SAE in tables and listings, and flagged as 'always serious' in AE listings.

An overview table will include the following

- Number of TEAEs,
- Number and percentage of subjects with TEAEs,
- Number of drug related TEAEs,
- Number and percentage of subjects with causally drug related TEAEs,
- Number of serious TEAEs,

- Number and percentage of subjects with serious TEAEs,
- Number of serious drug related TEAEs,
- Number and percentage of subjects with serious drug related TEAEs,
- Number of TEAEs leading to permanent discontinuation of study drug,
- Number and percentage of subjects with TEAEs leading to permanent discontinuation of study drug, and
- Number of deaths.

In order to adjust for differences in subjects' durations and the potential differential dropout rates between the treatment groups, an overview table to report exposure adjusted incidence rate (per 100 subject-years) for the above AE categories will be summarized. The total subject-years of exposure is calculated as the sum over subjects of the total duration of exposure divided by 365.25:

$$\sum_{i} \frac{ld_i - fd_i + 1}{365.25},$$

where fd_i and ld_i denote the first dose date of study drug and the last dose date of study drug for subject *i*.

The number and percentage of subjects with TEAEs in the following AE categories will be summarized for each treatment group by system organ class (SOC), high level term (HLT) and preferred term (PT):

- TEAEs
- drug related TEAEs.

The number and percentage of subjects with TEAEs in the following AE categories will be summarized by SOC and PT:

- serious TEAEs,
- drug related serious TEAEs,
- TEAEs leading to permanent discontinuation of study drug,
- drug related TEAEs leading to permanent discontinuation of study drug,
- TEAEs that equal to or exceed a threshold of 5.0% in any treatment group (threshold is based on PT).

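### SAP 6.5.5 leaves out of the primary endometrial rate a hyperplasia or cancer found only on a biopsy more than 30 days after last dose, and is unclear when an in-window biopsy also exists

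*SAP*

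**What the plan says.** SAP 4.3 makes the EH set the analysis set for the rates of hyperplasia, cancer and disordered proliferative endometrium, and refers to 6.5.5 for its criteria. Section 6.5.5 requires of every member that she was randomized and dosed and "had the postbaseline biopsy done within 30 days after the last dose of study drug". Two further conditions are joined to this by a conjunction:

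- an acceptable baseline biopsy; and
- either a satisfactory result on or after Day 326, or that she "had a postbaseline final diagnosis of hyperplasia, disordered proliferative or malignant prior to Day 326".

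Where a woman has several post-baseline biopsies and none is abnormal, the last satisfactory result inside the window is used. If any is abnormal, the more severe result is used, and here no window is mentioned. Each rate is reported with an exact (Clopper-Pearson) one-sided 95% upper bound.

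The benchmark is in SAP section 3. "The total of 1740 subjects are planned to be randomized 1:1:1", with an "assumed background rate of 0.26% such as for endometrial hyperplasia" and up to 60% of women without evaluable biopsy data. The aim is that "the point estimate for the rate of the event is less than or equal to 1" per cent and "the upper bound of the one-sided 95% confidence interval is less than or equal to 4" per cent.

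On timing, Protocol 5.6.1 says that for end-of-treatment (EOT) or early-discontinuation (ED) "biopsies that are evaluated as insufficient material or unevaluable, a retest biopsy will be required", without a maximum interval from last dose. Protocol 2.2.1 ties the ED biopsy to the discontinuation visit, also without one. SAP 6.5.1 draws adverse events of special interest from treatment-emergent events, defined as those "on or after first dose of study drug and 21 days after the last dose of study drug".

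**The concern.** The Day 326 exception shows that the SAP accepts an asymmetry: a negative must be late enough to be a valid one-year negative, while a positive counts whenever it is found. The 30-day upper limit does not follow that principle. It treats positives and negatives alike, so a confirmed hyperplasia or cancer can fall out of numerator and denominator on timing alone.

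These are primary endpoints with very few expected events, and each arm's rate is read against fixed figures. No planned analysis brings such a case back. The adverse-event-of-special-interest rates, on the SAP definition, close at 21 days, which is earlier than the biopsy limit.

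**Working it through.** **Reading the text case by case**

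1. *Only post-baseline biopsy is more than 30 days after last dose, negative.* Not in the EH set.
2. *Only post-baseline biopsy is more than 30 days after last dose, positive.* Not in the EH set. The Day 326 exception does not help, because it waives the one-year requirement and not the 30-day condition. For illustration, take last dose on Day 100 and biopsy on Day 131. The positive is before Day 326, but 131 − 100 = 31 days, so the 30-day condition fails.
3. *An in-window biopsy (normal or unevaluable) and a later positive, other conditions met.* She has a biopsy within 30 days. Read literally, the more-severe-result rule has no window, so she is counted as a case. If the window is meant to govern both halves of the rule, the late positive is ignored. The SAP does not settle which.

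**The plan's own figure**

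- Evaluable per arm: 580 × (1 − 0.60) = 232.
- Upper bound for x cases in n: the 0.95 quantile of a Beta(x + 1, n − x) distribution.

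At n = 232:

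| Cases | Rate | Upper bound |
|---|---|---|
| 1 | 0.43% | 2.03% |
| 2 | 0.86% | 2.69% |
| 3 | 1.29% | 3.31% |
| 4 | 1.72% | 3.90% |
| 5 | 2.16% | 4.48% |

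The largest count meeting both limits is 2. The 1% limit decides; the 4% limit would fail only at 5 cases. With X binomial(232, 0.0026), P(X ≤ 2) = 97.7%, which reproduces the stated probability of more than 95%.

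**Effect of restoring one omitted case**

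The restored woman joins numerator and denominator. At the planned worst case, 2/232 = 0.86% (bound 2.69%) becomes 3/233 = 1.29% (bound 3.29%). The 1% figure is exceeded and the 4% figure still holds.

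Over other evaluable numbers, starting from the largest count that meets both limits:

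| Evaluable n | Before | After | Bound after |
|---|---|---|---|
| 290 | 2/290 = 0.69% | 3/291 = 1.03% | 2.64% |
| 348 | 3/348 = 0.86% | 4/349 = 1.15% | 2.60% |
| 464 | 4/464 = 0.86% | 5/465 = 1.08% | 2.25% |
| 580 | 5/580 = 0.86% | 6/581 = 1.03% | 2.03% |

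**How often the count sits at the limit**

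One case changes the reading only if the counted number is exactly at the limit. At the planned 0.26%, P(X = 2) = 9.95% for n = 232, and P(X = 5) = 1.4% for n = 580.

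**Does the rule bias the rate?**

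If a share q of all N women is late regardless of result, the expected rate in those who remain is p(1 − q)N / [(1 − q)N] = p. The rate is unchanged and only n falls. Downward bias needs a larger late share among positives than among negatives, and the documents give no figure for either.

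**The case against.** The strongest defence rests on the schedule. The EOT window is −14/+6 days, the last dose is due the day before visit 15, and the biopsy is required at the EOT or discontinuation visit. Follow-up is 3 weeks after last dose ± 3 days, so at most 21 + 3 = 24 days, and the 30-day limit runs beyond it. The amendment rationale says the wider EOT window lets a retest fall inside it. SAP version 2.0 lengthened the biopsy window, and ultrasound and DXA also use 30 days. This makes a first biopsy after day 30 look uncommon. It does not rule one out, because neither the ED biopsy nor the retest has a stated maximum interval from last dose.

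A reader might infer that every late positive is lost. The text does not support that: a retest or work-up biopsy often follows an in-window sample, and the literal wording then keeps the woman and counts her positive.

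A reader might also infer that the primary rate is biased downward. That is not shown either, since late negatives go too.

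The rule is pre-specified and the same in every arm. That protects comparisons between arms, but it does not settle how a single arm's rate reads against a fixed 1%.

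Late cases are not invisible. Protocol 5.8.6 requires prompt notification of later events judged possibly related, and Protocol 7.6.1 also carries a treatment-emergent definition running to the last scheduled procedure. Neither puts the case in the primary rate.

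Finally, admitting late positives but not late negatives selects on outcome, and a late case may have arisen off drug. That is a fair reason not to make such a rule primary. It is not a reason against a labelled sensitivity analysis.

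**Conclusion.** The point holds in a limited form. A hyperplasia or cancer found only on a biopsy more than 30 days after last dose, in a woman with no in-window post-baseline biopsy, is excluded from the primary endometrial rate. For a woman with both, the SAP is ambiguous. At 232 evaluable women and a count of 2, one such case is the difference between 0.86% and 1.29%.

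This rests on the planned 60% non-evaluable share and on the count being at the limit. How many cases would be found late is unknown from the documents, so no probability can be put on the loss. It would also be too strong to say that an omitted case turns a failed trial into a passed one: the 1% and 4% figures stand in the sample-size text, and 6.5.5 reports rates and bounds without a pass/fail rule. This is a low-cost improvement to a primary safety endpoint, not a defect that undermines it.

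**What to change.** In SAP 6.5.5, before unblinding:

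1. Add a sensitivity analysis, by arm with Clopper-Pearson upper bounds, that admits and counts every post-baseline final diagnosis of hyperplasia or cancer regardless of time since last dose. The 30-day condition stays for negatives, and the present EH-set analysis stays primary. This extends the principle already used for diagnoses before Day 326.
2. State that the rule taking the more severe result is not limited by the 30-day window.
3. List by arm every positive found more than 30 days after last dose.

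The cost is a few lines of SAP text, one extra table and one listing. The added analysis may count a case that arose off drug, which makes it conservative. The placebo arm, handled the same way, gives the reference. Protocol 7.6.6 already leaves the biopsy window to the SAP, so the change can be made there.

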All biopsies will be read concurrently by 3 independent expert pathologists from institutions with independent fiduciary and organizational reporting. Each pathologist should be blinded to the treatment group and to the readings of the other pathologists. For EOT/ED biopsies and all biopsies in cases of uterine bleeding during treatment the concurrence of 2 of the 3 pathologists is accepted as the final diagnosis. If there is no agreement among the 3 pathologists, the most severe pathologic diagnosis should be used as the final diagnosis.

The 3 independent expert pathologists should use the same standardized criteria for the diagnosis of endometrial hyperplasia or endometrial cancer, and endometrial polyps should be fully characterized as to glandular proliferation and atypia. The standardized criteria for histologic evaluation can be viewed in the FDA Draft Guidance for Industry, Estrogen and Estrogen/Progestin Drug Products to Treat Vasomotor Symptoms and Vulvar and Vaginal Atrophy Symptoms – Recommendations for Clinical Evaluation, 2003.

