5 ENDPOINTS

5.1 Primary Safety Endpoint

The primary variable will require the evaluation of the effect of fezolinetant on the following:

- Frequency and severity of AEs.
- Percentage of subjects with endometrial hyperplasia.
- Percentage of subjects with endometrial cancer.

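### Counting only each woman's more severe endometrial result drops a woman with hyperplasia on one biopsy and cancer on another from the hyperplasia percentage, so that rate can look better because a case progressed

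*SAP*

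**What the plan says.** SAP 5.1 lists "Percentage of subjects with endometrial hyperplasia" as a primary safety variable, and the matching percentage for endometrial cancer as another. SAP 6.5.5 gets from biopsies to these percentages in three steps.

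- **Biopsy to diagnosis.** Two of three pathologists agreeing gives the final diagnosis. Failing that: "If there is no agreement among the three pathologists, the most severe diagnosis will then be used as the final diagnosis". Protocol 5.6.1 has the same tie-break: "the most severe pathologic diagnosis should be used as the final diagnosis".
- **Woman to result.** With several post-baseline biopsies and no abnormal final diagnosis, the last satisfactory result in the window is used; "otherwise, the more severe result will be counted".
- **Result to rate.** "For percentage of subjects with final diagnosis of endometrial hyperplasia, percentage of subjects with endometrial cancer, and percentage of subjects with disordered proliferative endometrium", the SAP says that "the exact (Clopper-Pearson) upper one sided 95% confidence interval will be provided".

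The denominator is the EH set. A woman without a satisfactory biopsy from Day 326 onwards can still qualify if she "had a postbaseline final diagnosis of hyperplasia, disordered proliferative or malignant prior to Day 326", provided the other conditions are met.

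SAP 3 justifies the number of evaluable women. At an assumed background rate of 0.26%, with hyperplasia as the example, the trial should be able to show that "the point estimate for the rate of the event is less than or equal to 1" percent and that the one-sided 95% upper bound is at most 4%. The stated probability is above 95%, allowing for up to 60% of women without evaluable biopsy data. Protocol 7.1 gives the same targets with a probability of at least 95%.

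The SAP text does not rank the diagnoses by severity. It does not say whether a woman counted under cancer is also counted under hyperplasia, and it names no combined hyperplasia-or-cancer rate on the EH set.

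**The concern.** More than one post-baseline biopsy per woman is built into the design: Protocol 2.2.1 and 5.6.1 require a biopsy for uterine bleeding as well as at end of treatment or early discontinuation. Suppose a bleeding-triggered biopsy gives a final diagnosis of hyperplasia and a later qualifying biopsy gives cancer. Under the one-result rule she is counted as cancer. She did have hyperplasia, and she remains in the EH set, but she no longer contributes to the hyperplasia percentage.

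The direction is the problem. A primary safety rate should not fall because a patient's condition worsened. Hyperplasia is also the event that the plan uses to illustrate its only numerical targets for endometrial safety, and at the planned number of evaluable women those targets turn on single cases.

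**Working it through.** **Inputs.** 580 women per arm, up to 60% without evaluable data, background rate 0.26%, targets 1% and 4% (SAP 3); one-sided 95% Clopper-Pearson bound and one counted result per woman (SAP 6.5.5). Assumed: cancer ranks above hyperplasia, and both biopsies have a final diagnosis and fall in the analysis window.

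**Step 1: evaluable women per arm.** 580 × (1 − 0.60) = 232.

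**Step 2: which counts meet the targets.** For x cases in n women the upper bound is the 95th percentile of a Beta(x + 1, n − x) distribution. At n = 232:

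| Cases | Rate | Upper bound | Rate ≤ 1% | Bound ≤ 4% |
|---|---|---|---|---|
| 1 | 0.43% | 2.03% | yes | yes |
| 2 | 0.86% | 2.69% | yes | yes |
| 3 | 1.29% | 3.31% | no | yes |
| 4 | 1.72% | 3.90% | no | yes |
| 5 | 2.16% | 4.48% | no | no |

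The 1% target binds, and the largest count that meets both is 2.

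**Step 3: reproduce the plan's figure.** P(X ≤ 2) for a binomial with n = 232 and p = 0.0026 is 0.5466 + 0.3306 + 0.0995 = 0.9767. That is 97.7%, consistent with the stated probability above 95%.

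**Step 4: apply the counting rule.** Take three women with a final diagnosis of hyperplasia, one of whom also has a final diagnosis of cancer.

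- SAP rule: hyperplasia 2/232 = 0.86% (bound 2.69%) and cancer 1/232 = 0.43% (bound 2.03%). Each row is within both targets.
- Every woman with hyperplasia: 3/232 = 1.29% (bound 3.31%). Hyperplasia or cancer is the same 3/232. Both exceed 1%.

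One case also separates meeting from missing 1% at other evaluable numbers:

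| Evaluable | Largest count within 1% | One more case |
|---|---|---|
| 290 | 2 (0.69%) | 3 (1.03%) |
| 348 | 3 (0.86%) | 4 (1.15%) |
| 464 | 4 (0.86%) | 5 (1.08%) |
| 580 | 5 (0.86%) | 6 (1.03%) |

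**Step 5: how often it could matter.** Let p be the true rate of hyperplasia or worse and q the share of those cases counted under cancer. The documents give no value for q, so a range is shown. The chance that the hyperplasia row meets both targets at n = 232 is P(X ≤ 2) with event probability p(1 − q):

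| p | q = 0 | q = 10% | q = 20% | q = 50% |
|---|---|---|---|---|
| 0.26% (planned) | 97.7% | 98.2% | 98.7% | 99.6% |
| 1.0% (assumed) | 59.0% | 65.3% | 71.6% | 88.9% |

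At the planned rate, three or more cases have a probability of only 1 − 0.977 = 2.3% before any reclassification. The rule has a noticeable effect only if the true rate is well above plan.

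**The case against.** The strongest reply is that nothing is lost. One counted result per woman makes the rows mutually exclusive, and cancer is itself a primary variable with its own rate and bound. A reader can add 2/232 and 1/232 to get 3/232. This stands: a reader might infer that the rule conceals progressed cases, and it does not. What remains is that the row labelled as the percentage with hyperplasia omits a woman who had it, and the reader must know to do the addition.

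A reader might also infer that the trial can formally pass its primary endometrial criterion because a case progressed. The documents do not support that. The 1% and 4% figures appear only in the sample-size text (Protocol Synopsis and 7.1, SAP 3). Protocol 7.6.6 and SAP 6.5.5 promise rates and one-sided bounds without a pass/fail test.

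It is tempting to say that the three-pathologist tie-break does the same within one biopsy. With reads of hyperplasia, cancer and benign, cancer becomes the final diagnosis, but there was never a final diagnosis of hyperplasia to lose. That example does not support the point.

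Nor can it be said that no planned table shows a combined rate. SAP 6.1 leaves table layouts to separate specifications, which are not available here. The adverse event of special interest in SAP 6.5.1 does group hyperplasia and cancer and is summarised by preferred term, so a woman with both events reported could appear under each term. It also includes disordered proliferative endometrium, and it rests on adverse event reports rather than on the three-pathologist final diagnosis.

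Finally, the rate could be read as covering any biopsy with a final diagnosis of hyperplasia. That reading sits poorly with the preceding sentence, which selects one result per woman. If both readings are open, the primary rate depends on who programs it, which is itself a reason to clarify.

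**Conclusion.** The point holds with limited reach. As most naturally read, SAP 6.5.5 removes from the primary hyperplasia numerator a woman who also has a final diagnosis of cancer on another qualifying biopsy, while keeping her in the denominator. The effect runs in the favourable direction for hyperplasia, and the case remains visible under cancer.

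In the planned minimum of 232 evaluable women per arm, one such woman is the difference between 0.86% and 1.29%, either side of the 1% sample-size target; the 4% bound is met both ways. That switch needs the count to sit just above the limit and one of those women also to have cancer, so it should be rare at 0.26%. The conclusion rests on cancer ranking above hyperplasia and on the one-result reading. The shares moved to cancer in the illustration are assumptions.

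**What to change.** In SAP 6.5.5:

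1. State the severity order of the diagnoses.
2. Add a row for the percentage of EH-set women with a final diagnosis of hyperplasia or cancer on any qualifying post-baseline biopsy, with its one-sided 95% Clopper-Pearson bound. Name this row as the one to compare with the 1% and 4% targets in SAP 3.
3. Keep the separate hyperplasia, cancer and disordered proliferative rows, which then stay mutually exclusive. Add a footnote giving the number of women counted under cancer who also had a final diagnosis of hyperplasia.

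The cost is SAP wording, one table row and a footnote, all from data already collected. The rate compared with the targets can only stay the same or become slightly less favourable. If the 0.26% assumption covers hyperplasia alone, the probability of meeting the targets on the combined row is somewhat below 97.7%. The documents give no background rate for cancer, so SAP 3 should say which event the 0.26% describes.
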